8.3.7 Adverse event of special interest

An AESI is an AE (serious or nonserious) of scientific and medical concern specific to the Sponsor's product or program, for which ongoing monitoring and immediate notification by the Investigator to the Sponsor is required. Such events may require further investigation in order to characterize and understand them. Adverse events of special interest may be added, modified, or removed during a study by protocol amendment.

- Anaphylactic reactions
- Systemic hypersensitivity reactions
- Helminthic infections
- Any severe type of conjunctivitis or blepharitis
- Keratitis
- Clinically symptomatic eosinophilia (or eosinophilia associated with clinical symptoms)
- Significant ALT elevation
 - ALT $>5 \times$ the ULN in participants with baseline ALT $\leq 2 \times$ ULN;
or
 - ALT $>8 \times$ ULN if baseline ALT $>2 \times$ ULN.
- Pregnancy of a female participant entered in a study as well as pregnancy occurring in a female partner of a male participant entered in a study with IMP.
 - Pregnancy occurring in a female participant entered in the clinical study or in a female partner of a male participant entered in the clinical study. It will be qualified as an SAE only if it fulfills one of the seriousness criteria (see Appendix 3 [[Section 10.3](#)]).
 - In the event of pregnancy in a female participant, IMP should be discontinued.
 - Follow-up of the pregnancy in a female participant or in a female partner of a male participant is mandatory until the outcome has been determined (See Appendix 4 [[Section 10.4](#)])
- Symptomatic overdose (serious or nonserious) with IMP/Noninvestigational medicinal product (NIMP)

- An overdose (accidental or intentional) with the IMP is an event suspected by the Investigator or spontaneously notified by the participant (not based on systematic pills count) and defined as at least twice the intended dose during an interval of less than 11 days. The circumstances (ie, accidental or intentional) should be clearly specified in the overdose form. An overdose (accidental or intentional) with any NIMP is an event suspected by the Investigator or spontaneously notified by the participant (not based on systematic pills count) and defined as at least twice the maximum prescribed daily dose, within the intended therapeutic interval. The circumstances (ie, accidental or intentional) should be clearly specified in the overdose form.

8.3.7.1 *Anaphylactic reactions*

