8.4 TREATMENT OF OVERDOSE

Symptomatic overdose (serious or nonserious) with IMP/NIMP is considered as an AESI (defined in [Section 8.3.7](#)). No antidote is available for dupilumab. The Sponsor does not recommend specific treatment for an overdose.

In the event of an overdose, the Investigator/treating physician should:

1. Contact the Sponsor immediately.
2. Closely monitor the participant for any AE/SAE and laboratory abnormalities until dupilumab can no longer be detected systemically (at least 98 days).
3. Obtain a plasma sample for PK analysis as soon as possible from the date of the last dose of IMP if requested by the Sponsor (determined on a case-by-case basis).
4. Document appropriately in the eCRF.

Decisions regarding dose interruptions will be made by the Investigator in consultation with the Sponsor based on the clinical evaluation of the participant.

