4.7.1 Extent of exposure

The extent of IMP exposure will be assessed by the duration of IMP exposure and compliance and summarized within the safety population.

Duration of IMP exposure

Duration of IMP exposure is defined as last dose date – first dose date + 15 days, regardless of unplanned intermittent discontinuations. If the date of the last dose of IMP is missing, the duration of IMP will be left as missing.

Duration of IMP exposure will be summarized descriptively as a quantitative variable (number, mean, SD, median, minimum, and maximum). In addition, duration of IMP exposure will also be summarized categorically by numbers and percentages for each of the following categories and cumulatively according to these categories:

- >0 and \leq 2 weeks
- >2 and \leq 4 weeks
- >4 and \leq 8 weeks
- >8 and \leq 12 weeks
- >12 and \leq 16 weeks
- >16 and \leq 20 weeks
- >20 and \leq 24 weeks
- >24 weeks and \leq 24 weeks + 3 days
- >24 weeks + 3 days

Additionally, the cumulative duration of IMP exposure will be provided, defined as the sum of the duration of treatment exposure for all participants, and will be expressed in participant years.

Treatment compliance

A given administration will be considered noncompliant if the participant did not take the planned dose as required by the protocol. No imputation will be made for participants with missing or incomplete data.

Percentage of treatment compliance for a participant will be defined as the number of administrations that the participant was compliant divided by the total number of administrations that the participant was planned to take from the first administration of IMP up to the actual last administration of IMP.

Treatment compliance will be summarized quantitatively and categorically: <80%, \geq 80%.

Cases of overdose (defined as at least twice the intended dose during an interval of less than 11 days) are considered an AESI and will be listed as such.

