Analysis of all adverse events

The overview of TEAE with the details below will be generated:

- Any TEAE
- Any severe TEAE
- Any treatment emergent SAE
- TEAE leading to death
- Any TEAE leading to permanent intervention discontinuation
- Any treatment emergent AESI
- Any treatment emergent other AE of interest grouping
- Any TEAE related to IMP

The AE summaries of **Table 6** will be generated with number (%) of participants experiencing at least one event.

Table 6 - Analyses of adverse events

Type of AE	MedDRA levels
All TEAE	Primary SOC, HLGT, HLT and PT
	Primary SOC and PT
	PT
	Primary and secondary SOC, HLGT, HLT and PT
Common TEAE $\geq 5\%$ in any group)	Primary SOC and PT
TEAE related to IMP as per Investigator's judgment	Primary SOC, HLGT, HLT and PT
	Primary SOC and PT
TEAE by maximal intensity	Primary SOC and PT
Treatment emergent SAE	Primary SOC, HLGT, HLT and PT
	Primary SOC and PT
Treatment emergent SAE related to IMP as per Investigator's judgment	Primary SOC, HLGT, HLT and PT
TEAE leading to permanent intervention discontinuation	Primary SOC, HLGT, HLT and PT
	Primary SOC and PT
TEAE leading to death (death as an outcome of the AE as reported by the Investigator in the AE page)	Primary SOC, HLGT, HLT and PT
Pretreatment AE	Overview ^a
	Primary SOC and PT

^a Will include the following AE categories: any AEs, any serious AEs, any AEs leading to death, any AEs leading to permanent intervention discontinuation

In addition, the exposure adjusted incidence rate of TEAEs by primary SOC and PT will be generated, showing the number of participants with at least one TEAE per 100 patient-years. For participants with an event, patient-years will be calculated up to the first event, and for participants without an event, patient-years will correspond to the length of the TE period.

Risk differences (constructed using the Miettinen and Nurminen method) and hazard ratios (Cox proportional hazards model) for dupilumab versus placebo with corresponding 95% CIs will be provided for the common TEAEs (PT \geq 5% in any intervention group). Participants without an event will be censored at the end of the treatment-emergent period in the Cox model. Forest plots will also be presented.

Analysis of deaths

In addition to the analyses of deaths included in [Table 5](#) the number (%) of participants in the following categories will be provided:

- Deaths during the treatment-emergent and post-treatment periods

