- Deaths in non-randomized or randomized but not treated participants

Analysis of adverse events of special interest (AESIs) and other AEs of interest

Adverse events of special interest (AESIs) and other AEs of interest will be selected for analyses as indicated in [Table 7](#). Number (%) of participants experiencing at least one event will be provided for each event of interest. Tables will be sorted as indicated in [Table 5](#).

Table 7 - Selections for AESIs and other AEs of interest

AE Grouping	Criteria
AESI	
Anaphylactic reaction	Anaphylactic reaction algorithmic approach (Introductory Guide for Standardised MedDRA Queries (SMQs) Version 18.1): includes anaphylactic reaction narrow SMQ (20000021) terms and programmatic identification of cases based on occurrence of at least two preferred terms meeting the algorithm criteria occurring within 24 hours of each other. The latter cases identified using the algorithm will undergo blinded medical review taking into account the timing of events relative to each other and to IMP administration for final determination of an anaphylactic reaction or not.
Systemic hypersensitivity reactions	SMQ [20000214] hypersensitivity narrow search and [AE corrective treatment/therapy = 'Y' or Action taken with IMP = 'Drug withdrawn' or Action taken with IMP = 'Drug interrupted'] followed by blinded medical review (documented process) for selection of relevant systemic hypersensitivity events
Helminthic infections	CMQ10544 based on HLGT as "Helminthic disorder"
Any severe type of conjunctivitis	CMQ10498 based on PTs (See Section 5.5) ^a and "Severe" ticked in Adverse Events eCRF page
Any severe type of blepharitis	CMQ10497 based on HLGT as "Lid, lash and lacrimal infections, irritations and inflammations" and "Severe" ticked in Adverse Events eCRF page
Keratitis	CMQ10642 based on the following PTs [keratitis, allergic keratitis, ulcerative keratitis, atopic keratoconjunctivitis, herpes ophthalmic, ophthalmic herpes simplex, corneal infection] ^a

AE Grouping	Criteria
Clinically symptomatic eosinophilia (or eosinophilia associated with clinical symptoms) ^b	CMQ10641 based on HLT = Eosinophilic disorders or PT = Eosinophil count increased
Pregnancy of a female patients entered in a study as well as pregnancy occurring in a female partner of a male patient entered in a study with IMP/NIMP	"Pregnancy" or "Partner Pregnancy" checked on the Pregnancy eCRF page as reported by the investigator

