Significant ALT elevation	ALT >5 x ULN in participants with baseline ALT ≤2 x ULN; OR ALT >8 x ULN if baseline ALT >2 x ULN
Symptomatic overdose with IMP	Symptomatic Overdose is answered Yes, with Overdose of IMP answered Yes on AE eCRF.
Symptomatic overdose with NIMP	Symptomatic Overdose is answered Yes, with Overdose of NIMP answered Yes on AE eCRF.
Other selected AE Grouping	
Serious injection site reactions or severe injection site reactions that last longer than 24 hours	HLT = 'Injection site reactions' and either with serious status, or with severe status and (AE end date/time - AE start date/time) ≥24 hours or ongoing
Severe or serious infection	Primary SOC = 'Infections and infestations' and with severe or serious status
Drug-related hepatic disorder	SMQ [20000006] Drug-related hepatic disorders- narrow
Injection site reaction	HLT = 'Injection site reactions'
Malignancy	SMQ [20000091]- Malignant or unspecified tumors narrow
Conjunctivitis (narrow)	CMQ10644 based on the following PTs [Conjunctivitis, Conjunctivitis allergic, Conjunctivitis bacterial, Conjunctivitis viral, Atopic keratoconjunctivitis] ^a
Conjunctivitis (broad)	CMQ10645 based on the following PTs [Conjunctivitis, Conjunctivitis allergic, Conjunctivitis bacterial, Conjunctivitis viral, Atopic keratoconjunctivitis, Blepharitis, Dry eye, Eye irritation, Eye pruritus, Lacrimation increased, Eye discharge, Foreign body sensation in eyes, Photophobia, Xerophthalmia, Ocular hyperaemia, Conjunctival hyperaemia] ^a
Conjunctivitis (FDA)	CMQ10643 based on the following PTs [Conjunctivitis, Conjunctivitis allergic, Conjunctivitis bacterial, Conjunctivitis viral, Eye irritation, Eye inflammation, Giant papillary conjunctivitis] ^a
Keratitis (FDA)	CMQ30102 based on the following PTs [keratitis, allergic keratitis, ulcerative keratitis, atopic keratoconjunctivitis, ophthalmic herpes simplex,] ^a

a The list of terms may be adjusted according to MedDRA version changes

b All cases of Eosinophilia will be included in the analysis, where cases associated with clinical symptoms will be further described in the CSR

The following summaries will be provided:

- All TEAEs, by selected standardized MedDRA query (SMQ)/Customized MedDRA query (CMQ) and PT or by laboratory values (as in alanine aminotransferase (ALT) elevation), showing the number (%) of participants with at least 1 PT,

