5.5 APPENDIX 5 SELECTION CRITERIA FOR AE/MEDICATION GROUPINGS

Table 12 - List of PTs or Medications for CMQs/CDGs

Grouping	Preferred Term/ Medication Code	Preferred Term/ Medication
Conjunctivitis	10001257	Adenoviral conjunctivitis
Conjunctivitis	10010725	Conjunctival irritation
Conjunctivitis	10010726	Conjunctival oedema
Conjunctivitis	10010736	Conjunctival ulcer
Conjunctivitis	10010741	Conjunctivitis
Conjunctivitis	10010744	Conjunctivitis allergic
Conjunctivitis	10010745	Conjunctivitis chlamydial
Conjunctivitis	10010749	Conjunctivitis gonococcal neonatal
Conjunctivitis	10010754	Conjunctivitis tuberculous
Conjunctivitis	10010755	Conjunctivitis viral
Conjunctivitis	10018258	Giant papillary conjunctivitis
Conjunctivitis	10021629	Inclusion conjunctivitis
Conjunctivitis	10030861	Ophthalmia neonatorum
Conjunctivitis	10048908	Seasonal allergy
Conjunctivitis	10049458	Herpes simplex virus conjunctivitis neonatal
Conjunctivitis	10051625	Conjunctival hyperaemia
Conjunctivitis	10053991	Inclusion conjunctivitis neonatal
Conjunctivitis	10061784	Conjunctivitis bacterial
Conjunctivitis	10062889	Pingueculitis
Conjunctivitis	10063669	Photoelectric conjunctivitis
Conjunctivitis	10067317	Oculorespiratory syndrome
Conjunctivitis	10067817	Acute haemorrhagic conjunctivitis
Conjunctivitis	10069166	Blebitis
Conjunctivitis	10071570	Ligneous conjunctivitis
Conjunctivitis	10074701	Noninfective conjunctivitis
Conjunctivitis	10075264	Oculoglandular syndrome
Conjunctivitis	10080825	Conjunctivitis fungal
Conjunctivitis	10084034	Conjunctival suffusion

Grouping	Preferred Term/ Medication Code	Preferred Term/ Medication
Intravenous immunoglobulin therapy	CAS 8000012671	IMMUNOGLOBULIN HUMAN NORMAL
Intravenous immunoglobulin therapy	CAS 8000050682	IMMUNOGLOBULIN, PORCINE
Intravenous immunoglobulin therapy	CAS 8000056919	IMMUNOGLOBULIN G HUMAN
Intravenous immunoglobulin therapy	CAS 8600000563	IMMUNOGLOBULINS NOS
Intravenous immunoglobulin therapy	CAS 8600001670	IMMUNOGLOBULIN HUMAN NORMAL SLRA
Intravenous immunoglobulin therapy	CAS 8600001671	IMMUNOGLOBULIN HUMAN NORMAL IFAS
Intravenous immunoglobulin therapy	RECNO 900708	OTHER IMMUNOGLOBULINS
Intravenous immunoglobulin therapy	RECNO 900722	IMMUNE SERA AND IMMUNOGLOBULINS
Intravenous immunoglobulin therapy	RECNO 900728	IMMUNOGLOBULINS
Intravenous immunoglobulin therapy	RECNO 900914	SPECIFIC IMMUNOGLOBULINS
Intravenous immunoglobulin therapy	RECNO 901112	IMMUNOGLOBULINS, NORMAL HUMAN

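### SAP Table 7 fills an AESI row titled as symptomatic eosinophilia with every eosinophilia adverse event, so the row and the any-AESI line can count participants who do not meet the protocol's AESI

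*SAP*

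**What the plan says.** **Eosinophilia.** The AESI list in protocol 8.3.7 contains "Clinically symptomatic eosinophilia (or eosinophilia associated with clinical symptoms"), so symptoms are part of the definition. The same section says that AESIs are added, modified or removed by protocol amendment. SAP 4.7.2, Table 7, repeats the title and gives the selection rule as "CMQ10641 based on HLT = Eosinophilic disorders or PT = Eosinophil count increased". Footnote b to the row adds: "All cases of Eosinophilia will be included in the analysis, where cases associated with clinical symptoms will be further described in the CSR".

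**Use of the row.** SAP 4.7.2 says that AESIs are selected for analysis by Table 7. The selected groupings receive counts, exposure-adjusted rates, risk differences and hazard ratios with 95% confidence intervals. The overview of treatment-emergent events has a line for "Any treatment emergent AESI".

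**Overdose.** Protocol 8.4 says: "Symptomatic overdose (serious or nonserious) with IMP/NIMP is considered as an AESI". SAP 4.7.1 says: "Cases of overdose (defined as at least twice the intended dose during an interval of less than 11 days) are considered an AESI", with no mention of symptoms. The Table 7 rule for study drug is "Symptomatic Overdose is answered Yes, with Overdose of IMP answered Yes on AE eCRF", and the rule for non-investigational product has the same form.

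**The concern.** The eosinophilia row has a narrow title and a broad content. A reader of the safety tables will take its count as the number of participants with symptomatic eosinophilia, when it is the number with any eosinophilia adverse event.

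The distinction matters for this drug. Protocol 2.3.2 lists eosinophilia among the identified adverse drug reactions, describes the rise in count as transient and in keeping with the mechanism, and reserves the important potential risk for eosinophilia with clinical symptoms (there, in asthma patients). The row mixes a known effect on the count with the risk being monitored. That can suggest an AESI excess on dupilumab that the protocol's definition would not show, and a genuine symptomatic case would be hard to see among the others.

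**Working it through.** **1. Does Table 7 normally enforce the qualifier in a row's title?**

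| Table 7 AESI row | Qualifier in title | Enforced by the rule? |
|---|---|---|
| Conjunctivitis | severe | Yes, severity ticked on the event page |
| Blepharitis | severe | Yes, severity ticked on the event page |
| Overdose, study drug and other product | symptomatic | Yes, symptom question answered yes |
| Systemic hypersensitivity | systemic | Yes, blinded medical review |
| Eosinophilia | clinically symptomatic | No, coded term only |

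Among these rows, eosinophilia is the one that drops its own qualifier. Table 7 also has a section for other selected groupings. It already holds narrow and broad conjunctivitis groupings, separate from the severe conjunctivitis AESI.

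**2. Where do the extra cases go?** Table 7 defines the AESIs to be analyzed, and the overview line gives no other definition. A participant whose only qualifying event is symptom-free eosinophilia therefore enters the eosinophilia row, its risk difference and hazard ratio, and the any-AESI line.

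**3. Size.** The documents state no eosinophilia or AESI rate, so there is no plan figure to reproduce. The only input is the planned 39 participants per arm (SAP section 2).

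- One added participant: 1/39 = 2.6 percentage points in that arm.

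The rest is illustration under assumed rates. Let e_D and e_P be the proportions with a symptom-free eosinophilia event on dupilumab (2% to 10%) and placebo (0% to 2%). Let a be the proportion meeting a protocol-defined AESI, equal in both arms (0% to 10%) and independent of the former.

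- Expected added cases, 39 × e: on dupilumab 39 × 0.02 = 0.8 to 39 × 0.10 = 3.9; on placebo 0 to 39 × 0.02 = 0.8.
- Chance of at least one added case on dupilumab, 1 − (1 − e_D)^39: 1 − 0.98^39 = 55% to 1 − 0.90^39 = 98%.
- Spurious any-AESI difference: [1 − (1 − a)(1 − e_D)] − [1 − (1 − a)(1 − e_P)] = (1 − a)(e_D − e_P).

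| e_D v e_P | a = 10% | a = 0% |
|---|---|---|
| 2% v 0% | 1.8 points | 2.0 points |
| 5% v 0% | 4.5 points | 5.0 points |
| 5% v 2% | 2.7 points | 3.0 points |
| 10% v 2% | 7.2 points | 8.0 points |

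At the corners of the assumed ranges the difference is 0 (2% v 2%) and 10 points (10% v 0%, a = 0).

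**4. Overdose.** The Table 7 rules require symptoms, as the protocol does. Asymptomatic overdose therefore adds 0 cases to the Table 7 AESI rows and to the any-AESI line.

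**The case against.** The best defence is that the broad rule is open and permitted. Protocol 9.4.2 leaves the method of identifying AESIs to the SAP, and footnote b states what is counted. Over-inclusive capture errs against the sponsor's own product. SAP 4.7 makes the safety analysis descriptive with no testing, so no formal conclusion turns on this row. AESIs reported by the investigator, who works from the protocol's definition, are summarized separately, and symptomatic cases are to be described in the study report.

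Much of this stands, and it limits the consequence. It does not remove the point. A method of identification is not a change of definition, which protocol 8.3.7 reserves for an amendment. A footnote on one row does not correct that row's title, and it does not travel to the pooled overview line. A descriptive table with the wrong label can still mislead.

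Two stronger readings go too far. A reader might infer that the symptomatic rate will appear in no table. The separate investigator-reported summary contradicts that; what is missing is a Table 7 row for it. A reader might also infer that the row will consist of raw laboratory findings. It takes reported adverse events only. Under protocol 8.2.4 and 10.3.1 a laboratory change becomes one when the investigator judges it clinically relevant or significant, and eosinophil values are analyzed separately under SAP 4.7.3.1.

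**Conclusion.** The point holds for eosinophilia. The title and the protocol require symptoms, while the selection rule and footnote b do not, and the row feeds both the AESI comparisons and the any-AESI line. This follows from the text alone.

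The size is 2.6 percentage points per added participant at 39 per arm. How many would be added is unknown. Protocol 2.3.2 supports a direction towards dupilumab but gives no frequency, so the case counts and differences in the working rest on assumed rates. The consequence is a mislabelled descriptive safety result; no efficacy result or test is affected.

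Two further inferences are not supported. SAP 4.7.1 might be read as inflating AESI counts with asymptomatic overdoses. Table 7 selects the AESIs and requires symptoms, so that sentence affects a listing only, unless programmers follow it in place of the table. Nothing suggests that overdoses would fall mainly on one arm. A reader might also want "Seasonal allergy" struck from the conjunctivitis list in SAP 5.5. Beyond the name of the term the documents give no basis for that, and for the AESI it counts only when the event is marked severe.

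**What to change.** In SAP Table 7:

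- Move the present eosinophilia rule, unchanged, to the other selected groupings, under a title that says all eosinophilia events. It then feeds the overview line for other groupings of interest, so no information is lost.
- Limit the AESI row to those events confirmed as clinically symptomatic at blinded medical review before database lock, by a documented process as for systemic hypersensitivity.
- State that only this restricted row feeds the any-AESI line, and revise footnote b to match.

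Separately, reconcile the overdose sentence in SAP 4.7.1 with Table 7 and with protocol 8.3.7 and 8.4, which require symptoms. This is a wording correction and changes no Table 7 count.

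The cost is SAP wording and a blinded review of what should be a handful of cases. No new data are needed.

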4.7.3 Additional safety assessments

4.7.3.1 **Laboratory variables, vital signs and electrocardiograms (ECGs)**

The following laboratory variables, vital signs and electrocardiogram (ECG) variables will be analyzed. They will be converted into standard international units.

- Hematology:
 - Red blood cells and platelets and coagulation: hemoglobin, hematocrit, red blood cell count, platelet count
 - White blood cells: white blood cell count, neutrophils, lymphocytes, monocytes, basophils, eosinophils
- Clinical chemistry:
 - **Metabolism:** glucose, total cholesterol, total protein, creatine phosphokinase
 - **Electrolytes:** sodium, potassium, chloride, bicarbonate
 - **Renal function:** creatinine, blood urea nitrogen, uric acid

- **Liver function:** alanine aminotransferase, aspartate aminotransferase, alkaline phosphatase, lactate dehydrogenase, total bilirubin, albumin
- **Pregnancy test:** Serum β -human chorionic gonadotropin (all female participants) will be performed at screening (V1) in women of childbearing potential, and a urine pregnancy test will be performed at V2 and every 4 weeks thereafter.
- **Hepatitis screen:** hepatitis B surface antigen (HBs Ag), hepatitis B surface antibody (HBs Ab), hepatitis B core antibody (HBc Ab), hepatitis C virus antibodies (HCV Ab) will be tested at screening (V1). In case of results showing HBs Ag (negative) and HBc Ab (positive), an hepatitis B virus (HBV) deoxyribonucleic acid (DNA) testing will be performed and should be confirmed negative prior to randomization. In case of results showing HCV Ab (positive), an HCV ribonucleic acid (RNA) testing will be performed and should be confirmed negative prior to randomization.
- **HIV screen:** Anti-HIV-1 and HIV-2 antibodies will be tested at Visit 1
- Urinalysis:
 - **Urinalysis** will include specific gravity, pH, glucose, ketones, blood, protein, nitrite, leukocyte esterase, urobilinogen and bilirubin. In case the urine dipstick test result is abnormal, a urine sample should be sent into the central laboratory for microscopic and macroscopic examination.
- Vital signs: heart rate (beats per minute), systolic and diastolic blood pressure (mmHg) in a semi-supine or sitting position after 5 minutes rest, weight, respiratory rate (breaths per minute), temperature (degrees Celsius) and height (screening only)
- ECG variables: ECG assessments will be described as normal or abnormal

Data below the lower limit of quantitation/detection limit (LLOQ) will be replaced by half of the LLOQ, data above the upper limit of quantification will be replaced by ULOQ value.

Quantitative analyses

For all laboratory variables and vital signs variables above, descriptive statistics for results and changes from baseline will be provided for each analysis window, the last value and the worst value during the on-treatment period. These analyses will be performed using central measurements only (when available) for laboratory variables.

For all parameters, mean changes from baseline with the corresponding standard error will be plotted over time.

Analyses according to PCSA

Potentially clinically significant abnormality (PCSA) analyses will be performed based on the PCSA list currently in effect at Sanofi at the time of the database lock. For parameters for which no PCSA criteria are defined, similar analyses will be done using the normal range, if applicable.

Analyses according to PCSA will be performed based on the worst value during the treatment-emergent period, using all measurements (either local or central, either scheduled, nonscheduled or repeated).

For laboratory variables and vital signs variables above, the incidence of participants with at least one PCSA during the treatment-emergent period will be summarized regardless of the baseline level and according to the following baseline status categories:

- Normal/missing
- Abnormal according to PCSA criterion or criteria

Additional analyses for suspect drug-induced liver injury

The following additional analyses will be performed for drug-induced liver injury:

- Time to onset of the initial ALT or aspartate aminotransferase (AST) elevation ($>3 \times \text{ULN}$) and total bilirubin elevation ($>2 \times \text{ULN}$) during the treatment-emergent period will be analyzed using Kaplan-Meier method.
- A graph of the distribution of peak values of ALT versus peak values of total bilirubin during the treatment-emergent period will be provided.
- For each liver function test (e.g., ALT), participants having a PCSA (e.g., ALT $>5 \text{ ULN}$) will be summarized using the following categories: Returned to baseline PCSA status (or returned to value $\leq \text{ULN}$ in case of missing baseline) before last IMP dose, Returned to baseline PCSA status after last IMP dose, Never returned to baseline PCSA status, No assessment after elevation. This summary will be performed by categories of elevation (ALT $>3, >5, >10, >20 \text{ ULN}$).

